### **Stage two: patient population**

A sample of 30 participants will be recruited from consecutive patients referred to our NHS Tertiary Airways service for assessment for complex breathlessness and ILO. Participants will be asked at initial assessment, after they have consented to the laryngoscopy, if they would wish to undergo TLUS concurrently with their usual care of diagnostic laryngoscopy.

An information leaflet will be given, and written consent form completed with the patient by the PI. Written Information will be provided at the point of initial consultation (at least 48 hours before the planned procedure. Written consent will take place at the appointment for the Laryngoscopy (usual care for laryngoscopy), by the PI (CS). A witness will not be present. Consent will take place in a private booking-in room that is part of usual care for patients attending for laryngoscopy assessment for ILO). Patients have more than 48 hours to consider the information and decide if they would like to participate.

Patients who require an interpreter for their initial consultation will be provided with information via the interpreter of the study.

Patients will be informed that usual care will not be affected by their decision to participate or not, and that consent can be withdrawn at any point. If the patient finds dual assessment with laryngoscopy and TLUS too invasive or distressing, they can withdraw consent, and the TLUS will be stopped.

It is envisaged that the TLUS operator (PI) will perform the US assessment whilst another SLT completes the laryngoscopy (usual care) and works through the usual diagnostic laryngoscopy provocation protocol to induce symptoms. The US-operating SLT will take a note of settings to achieve image acquisition and will take note of vocal fold movements on an anonymised recording form with subject allocation number identified.

The SLT operators (TLUS and laryngoscopy) will be blinded to the images and results of the other assessment (either TLUS or laryngoscopy), as the screen for the Laryngoscopy system can be rotated away to be unobservable by the US-operator SLT. Following the procedure, the SLT conducting the US will leave the endoscopy theatre room to allow for usual debrief to occur with the patient (usual care). After this, the patient will be asked to complete a short questionnaire electronically to elicit their experience of TLUS.

<https://forms.office.com/pages/designpagev2.aspx?lang=en->

Following the clinical session, the results of the TLUS and laryngoscopy will be compared for outcome and record made (on the reporting form) of the assessments compared, and any false positive or negative results will be documented, along with ability to visualise either or both vocal folds (left and right).

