### **Primary aims:**

To perform analysis of the range of vocal fold movements on inspiration, using TLUS in healthy volunteers and patients referred to a tertiary airways service.

To assess the sensitivity, specificity and positive predictive value of the use of ultrasound in the assessment of ILO, using Laryngoscopy as reference standard.

To investigate the patient and healthy volunteer perspectives of TLUS assessment of the vocal cords.

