### **Data analysis:**

The outcomes of the TLUS and laryngoscopy assessments in stage one and stage two and will be analysed using SPSS. 2 x 2 tables will be generated to calculate values of sensitivity (whether a participant can be confirmed as having ILO, or mimicked ILO) and specificity (whether ILO, or mimicked ILO, can be ruled out for a participant), and confidence intervals for visualisation of the vocal folds using TLUS. In stage two, percentage agreement between TLUS and laryngoscopy for confirmation or non-confirmation of ILO will also be calculated.

The values, if available, for measurements of the distance between the arytenoids for healthy volunteers and patients during normal breathing, deep inspiration, and during ILO (mimic in stage 1 and actual in stage 2), will be analysed via a non-parametric comparison of means within SPSS.

Quantitative questionnaire data will be analysed using Microsoft Excel to generate mean values and ranges. Qualitative questionnaire data will be analysed using thematic analysis (Braun and Clarke, 2006), with themes generated to aid understanding of participants' experiences of the TLUS and laryngoscopy procedures.

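### The plan has no way to count stage-two scans stopped for distress, so tolerability and patient experience are likely to be overstated

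*Combined protocol and SAP*

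**What the plan says.** The section on the stage-two patient population sets the rule: "If the patient finds dual assessment with laryngoscopy and TLUS too invasive or distressing, they can withdraw consent, and the TLUS will be stopped". The trigger is the combined procedure, not TLUS alone, and the only stated consequence is that "they can withdraw consent, and the TLUS will be stopped". The same section plans the sample ("A sample of 30 participants will be recruited from consecutive patients referred to our NHS Tertiary Airways service"; Aims & Objectives makes 30 an upper limit). It places the experience questionnaire after the procedure and the debrief: "After this, the patient will be asked to complete a short questionnaire electronically to elicit their experience of TLUS". It also has the ability to see each vocal fold documented when the two assessments are compared.

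Patient experience is one of the Primary aims: "To investigate the patient and healthy volunteer perspectives of TLUS assessment of the vocal cords". Diagnostic accuracy is another.

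Under Data analysis, "2 x 2 tables will be generated to calculate values of sensitivity" and specificity, with confidence intervals for visualisation. Quantitative questionnaire answers are summarised as means and ranges.

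The supplied text does not say:
- whether data gathered before a stop are kept;
- whether a patient who stopped is still offered the questionnaire;
- whether that patient is replaced to reach 30;
- how a stopped scan enters the 2 x 2 table.

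**The concern.** Tolerability is much of the case for TLUS. The Background justifies the study partly because laryngoscopy is invasive and some people cannot tolerate it, and the statement on current practice looks ahead to a well-tolerated test for children. A patient who cannot complete the scan is therefore an important observation, yet the protocol treats the event only as a matter of consent.

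Someone recorded as having withdrawn consent, with no TLUS result, has no cell in a 2 x 2 table, and staff have no clear basis for sending a questionnaire. The natural default is that this patient leaves both datasets. Those who stop for distress are likely to hold less favourable views than those who finish, so the experience summary would be tilted in favour of TLUS. For a proposed triage test, an unfinished scan may also give no answer, which affects the share of patients it can classify.

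**Working it through.** The plan states no withdrawal rate, tolerability figure or expected accuracy, so there is no figure to reproduce. The following is illustration on stated assumptions.

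**Inputs**
- Stage-two size: 30, all assumed to start the scan.
- Number stopping, s: not given; 1, 3 and 6 are tried.
- Questionnaire scale: not in the supplied text. A 5-point scale is assumed, with completers averaging 4.5 and stoppers scoring 1.
- ILO cases: not given for this population. The Background cites 24% to 53% in severe asthma. Applied to 30, this gives 0.24 × 30 = 7.2 and 0.53 × 30 = 15.9, so about 7 to 16; 15 is also shown.
- TLUS sensitivity among completers: assumed near 80%.

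**Step 1: is a stop likely to occur?** The chance of at least one in 30 is 1 − (1 − p)^30. For p = 2%, 5% and 10% this is 45%, 79% and 96%.

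**Step 2: tolerability and experience.** Define tolerating as not stopped. Among completers the figure is (30 − s)/(30 − s) = 100% by construction. Over all started it is (30 − s)/30. The mean score with everyone counted is [4.5(30 − s) + 1·s]/30.

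| Stopped | Completers only | All started (exact 95% CI) | Mean, completers | Mean, everyone |
|---|---|---|---|---|
| 1 | 29/29 = 100% | 29/30 = 97% (83 to 99.9%) | 4.5 | 4.38 |
| 3 | 27/27 = 100% | 27/30 = 90% (73.5 to 98%) | 4.5 | 4.15 |
| 6 | 24/24 = 100% | 24/30 = 80% (61 to 92%) | 4.5 | 3.80 |

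If stoppers are left out, the error runs one way.

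**Step 3: sensitivity.** Let D be the ILO cases, w those stopped and t the true positives among completers. Completer sensitivity is t/(D − w). With all D counted, the worst case is t/D and the best case (t + w)/D.

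| D | w | Completers | Worst case | Best case |
|---|---|---|---|---|
| 7 | 2 | 4/5 = 80% | 4/7 = 57% | 6/7 = 86% |
| 15 | 3 | 10/12 = 83% | 10/15 = 67% | 13/15 = 87% |
| 16 | 3 | 10/13 = 77% | 10/16 = 62.5% | 13/16 = 81% |

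In each row the completer value lies between the bounds, so the bias can go either way.

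**Step 4: share of patients correctly classified.** If c completers are classified correctly and a stopped scan yields no result, the share is c/(30 − s) among completers and c/30 among all started. The ratio of the second to the first is (30 − s)/30, whatever c is. With s = 3 it is 27/30 = 0.90, so the completer figure would need to be reduced by a tenth. This assumes that every patient has a laryngoscopy result.

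**The case against.** Several points against the concern are sound.

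- **Exclusion is inferred.** No section says that data from patients who stop are discarded. The patient *can* withdraw; not every stop is defined as withdrawal of data. The questionnaire follows the procedure and debrief, with no stated condition that the scan was finished. The operator notes vocal fold movements on a form, so a stopped scan may already hold a reading.
- **A stop need not be a TLUS failure.** The distress may come from the laryngoscopy, which the Background calls invasive, or from the combination. If the laryngoscopy also ends early there may be no reference result, and no 2 x 2 table could include the patient.
- **Ordinary scan failures are covered.** Folds not seen in a completed scan are documented, and intervals for visualisation are planned. Only scans ended for distress are at issue.
- **The consent form is not available here** and may already separate the two decisions.

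A reader might go further and infer that TLUS will look more accurate than it is, because provocation makes stopping likeliest when ILO is present. The documents do not support that. They give no data on who stops. Losing more ILO patients does not by itself bias sensitivity, which is computed within ILO patients; bias needs stopping to be related to whether TLUS would have been right. One can build examples: with 15 ILO cases, 1, 2 or 3 stopped and one miss among completers, 13/14 = 93%, 12/13 = 92% and 11/12 = 92% become 13/15 = 87%, 12/15 = 80% and 11/15 = 73%. But the fall comes from scoring every stop as a miss.

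A reader might also infer that the rule in Study end definition on adverse patient feedback would miss the worst experiences. That rule refers to feedback generally, and stopping in distress in front of the operator could count.

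None of this supplies a rule for recording and counting stopped scans, and the tolerability point stands.

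**Conclusion.** The point holds as a gap with a predictable consequence for tolerability. Distress with the dual assessment is handled only through withdrawal of consent, and the analysis has no place for the resulting stopped scan. If those patients are lost, tolerability and patient experience are overstated: 100% against 97%, 90% or 80% if 1, 3 or 6 of 30 stop. These counts are assumptions; the true rate is unknown, and with no stops there is no effect.

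For accuracy the conclusion is weaker. The share of all started patients correctly classified may be overstated, but neither the direction nor the size of any bias in sensitivity or specificity among completers can be fixed from the documents. The change is worth making before recruitment, because reasons for stopping and permission to keep data are hard to recover afterwards.

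**What to change.** 1. In the stage-two section, and in the consent form if it does not already do so, separate the decision to stop the scan from the decision to withdraw consent for data use.
2. Record every stopped TLUS with its reason: TLUS, laryngoscopy or the combination. Report the proportion stopped, overall and by reason, over all scans started as a tolerability result.
3. Offer the questionnaire to patients who stop but do not withdraw data consent, and state how many of them answered.
4. Beside the completer 2 x 2 table, add an analysis over all started scans that have a laryngoscopy result. In the worst case a stopped scan counts as not detected where ILO is present and as not ruled out where it is absent; in the best case it counts as correct. State in advance whether a reading made before the stop is used.
5. Report patients who withdraw data consent only as a count, and say whether they are replaced to reach 30.

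The cost is protocol wording, possibly consent wording, one extra field on the recording form and one extra table. The headline figure may be less favourable. The patient's right to stop is unchanged.

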A record will be taken of the frequency in MHz and depth that successful visualisation of the vocal cords occurred to help inform future studies and refine the protocol. Any other factors that are deemed useful to include to help replicate findings and improve image quality and scanning success will also be recorded (such as gain used, high or low, and approach transverse, or lateral longitudinal, and the use of any pre-sets such as Neo-head, lung or small parts).

When the vocal cords are visualised, the healthy volunteer will be asked to breathe normally, take 3 deep inspirations, and then, say “ee” for a sustained period. They will then be asked to breath hold, then take a deep breath in (3 trials), and then mimic ILO (the PI will discuss how to do this before the scan takes place). The commands for each of the above will be in the same order for each patient, as there is no accompanying sound, this will allow for easier analysis to be able to differentiate each vocal cord movement according to what the volunteer was asked to do.

Following the procedure, the volunteer will be given an electronic questionnaire to complete, so that feedback on their experience can be gained and used as part of writing up of findings.

[https://forms.office.com/pages/designpagev2.aspx?lang=en-US&origin=OfficeDotCom&route=Start&subpage=design&id=gmOokJ\\_8nEW5GphS-wiyzcd-VqpQSdVGguxTgVT2MfRUMEZUNUoxT1YyQkIPOEVVM0VQVVpJRUVEUS4u](https://forms.office.com/pages/designpagev2.aspx?lang=en-US&origin=OfficeDotCom&route=Start&subpage=design&id=gmOokJ_8nEW5GphS-wiyzcd-VqpQSdVGguxTgVT2MfRUMEZUNUoxT1YyQkIPOEVVM0VQVVpJRUVEUS4u)

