**Data collection and handling:**

Written recording forms will be marked with an anonymous participant code. Data from recording forms for stage one and stage two will be extracted and inputted into the SPSS statistical analysis package by the PI. Recording forms will be stored in a locked filing cabinet in the SLT NHS office.

Data from participant questionnaires from stage one and stage two will be downloaded from Microsoft Forms into a Microsoft Excel database. All digital database files will be stored on a password-protected NHS laptop. Long-term arrangements: Study documents including data and investigator site files will be archived at the Trust's off site archiving facility following local procedures.

The Vscan Air ultrasound system allows clinicians to securely share data and images and includes sharing auto-anonymized images with other apps, with no cloud requirement.

Images will be stored on a NHS laptop which is password protected and will be stored in a password-protected file.

All data will be anonymised via a combination of identifier as a healthy volunteer (HV) or patient (PT) and participant number, followed by the date of clinic (e.g HV1 18.07.22, or for patients PT118.07.22).

Data for healthy volunteer and patients will be analysed by the Principal Investigator electronically on an NHS laptop.

Advice will be sought from LTHTR research team regarding support for statistical analysis of data, but all patient identifiable data will be removed before this stage.

Research data will be stored electronically, which will comprise scanned consent forms and questionnaires, US and laryngoscopy images, examination data recording sheets and statistical data. Electronic data will be stored on the NHS Trust server in a password-protected folder, accessed only by the Principal Investigator.

Study documents including data and investigator site files will be archived at the Trust's off site archiving facility following local procedures.

Identifiable personal data for the healthy volunteers or the patient participants will not be used for either stage 1 or 2.

Healthy volunteer consent forms and any data will be kept in a separate file, and no access to medical records will be made for these patients. The local SOP for Research with Health Volunteers will be followed.

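### Turning the laryngoscopy screen away leaves the TLUS operator open to symptom and speech cues during provocation, and no masked reading of the stage two scans is planned

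*Combined protocol and SAP*

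**What the plan says.** All of this comes from the Combined protocol and SAP.

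- **Blinding (Stage two: patient population).** The two operators "will be blinded to the images and results of the other assessment (either TLUS or laryngoscopy"). The mechanism given is the laryngoscopy screen, "as the screen for the Laryngoscopy system can be rotated away to be unobservable by the US-operator SLT".
- **Timing (same section).** The PI scans while a second therapist performs the laryngoscopy and "works through the usual diagnostic laryngoscopy provocation protocol to induce symptoms". The PI's departure comes only afterwards: "Following the procedure, the SLT conducting the US will leave the endoscopy theatre room to allow for usual debrief".
- **TLUS record (same section).** The scanning operator "will take note of vocal fold movements on an anonymised recording form with subject allocation number identified".
- **Comparison (last paragraph on stage two).** After the clinical session the two results are compared, and false positives and false negatives are written down.
- **Use of the result.** Primary aims lists sensitivity, specificity and positive predictive value against laryngoscopy. Data analysis builds the 2 x 2 tables and, for stage two, percentage agreement.
- **Stored material.** Data collection and handling lists "US and laryngoscopy images, examination data recording sheets and statistical data". The stage one section describes the scan recordings with the remark "as there is no accompanying sound".
- **Second readers.** The stage one section sends a proportion of scans to a collaborator and a specialist sonographer, to settle uncertain findings and check inter-rater reliability. The stage two section has no equivalent.

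**The concern.** An accuracy study of an imaging test needs the index reading to be made without information that tracks the reference result, other than the image itself. Here the reference procedure works by provoking symptoms, and the index operator is at the patient's neck while it happens. Hiding a screen removes one channel. The patient's breathing or distress, the provocation steps and anything the laryngoscopist says remain.

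If the PI is unsure of an image and leans on those cues, the 2 x 2 table credits ultrasound with information that came from elsewhere. A primary aim is the accuracy of ultrasound for ILO, and the pilot is meant to inform further studies. With no stage two reading made from the image alone, the planned analysis cannot separate the two sources.

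**Working it through.** The plan gives no figure to reproduce: the stage two size of 30 has no stated precision or power basis. The check has two parts.

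**1. What each safeguard covers**

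| Possible cue | Safeguard in the documents |
|---|---|
| Laryngoscopy image | Screen rotated away |
| Laryngoscopy result after the procedure | PI leaves before the debrief |
| Symptoms provoked during the scan | None stated |
| Laryngoscopist's speech during the scan | None stated |
| Reading from the image alone, afterwards | Not planned for stage two |

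**2. Direction and possible size (illustration only)**

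Let f be the share of TLUS calls that follow the symptoms. Then:

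- observed Se = (1 − f) × Se(image) + f × Se(symptoms), and the same form for Sp;
- LR+ = Se / (1 − Sp), which fixes PPV at a given prevalence p;
- change in agreement = p × (change in Se) + (1 − p) × (change in Sp).

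Assumed, not from the documents: image-only Se 0.60 and Sp 0.80, and the symptom values below. For p, the range 0.24 to 0.53 is borrowed from the Background figure for severe asthma; the stage two case mix may differ.

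| f | Symptom Se / Sp | Observed Se | Observed Sp | LR+ | Agreement change, p = 0.24 (points) | p = 0.53 (points) |
|---|---|---|---|---|---|---|
| 0 | – | 0.60 | 0.80 | 3 | – | – |
| 0.25 | 0.90 / 0.70 | 0.675 | 0.775 | 3 | −0.1 | +2.8 |
| 0.50 | 0.90 / 0.70 | 0.75 | 0.75 | 3 | −0.2 | +5.6 |
| 0.50 | 0.90 / 0.90 | 0.75 | 0.85 | 5 | +7.4 | +10.3 |
| 0.50 | 0.80 / 0.50 | 0.70 | 0.65 | 2 | −9.0 | −1.75 |

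Worked line, third row: Se = 0.5 × 0.60 + 0.5 × 0.90 = 0.75; Sp = 0.5 × 0.80 + 0.5 × 0.70 = 0.75; LR+ = 0.75 / 0.25 = 3. The change in agreement is 0.15p − 0.05(1 − p), which is positive only if p exceeds 0.25.

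Sensitivity rises in every row because the symptoms were assumed more sensitive than the image. Specificity, LR+ (hence PPV) and agreement go up, down or nowhere, depending on how well symptoms discriminate.

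**3. Scale against sampling error**

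If the 30 patients split 15 and 15, a 15-point shift in sensitivity is 0.15 × 15 = 2.25 patients. An observed 12 of 15 has an exact 95% interval of 52% to 96%. A shift of this size would not stand out in the planned table.

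**The case against.** Four points can fairly be made on the other side.

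- **Intended use.** TLUS is proposed as a bedside triage tool, where the operator would see the patient anyway. A live reading blinded to laryngoscopy is a defensible target for a pilot. This stands, and is why the live call should be kept and reported, not replaced.
- **What is inferred.** The protocol does not say outright that the ILO call is made at the bedside; it says that the operator notes vocal fold movements. It lists no audible or visible signs of ILO, saying only that symptoms resemble asthma. No section says how strongly provoked symptoms track the diagnosis. This also stands. Even so, the scanning operator's form is the only stage two TLUS record described.
- **External readers.** They exist, but under stage one, for a proportion of scans, and their reading is not made the index result. This does not close the gap.
- **Risk in a re-read.** If the PI re-read clips after results had been compared session by session, the PI would probably already know the laryngoscopy findings, which could be a worse bias. This stands and governs the order of steps in the fix.

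A reader might infer that the bias will raise sensitivity and agreement together, by some 15 points for sensitivity. The documents do not support that. The 15 points rest on assumed inputs, under which PPV is unchanged, specificity falls 5 points and agreement rises only above 25% prevalence. A reader might also count the PI's role in consent and knowledge of the referral as cues. Every participant is referred for breathlessness and ILO assessment and consented by the PI, so this alone does not separate patients with ILO from those without.

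**Conclusion.** The point holds in a limited form. The stated blinding does not extend to symptoms or speech during provocation, and no masked stage two reading is planned, so the TLUS result may partly reflect bedside cues. This can raise sensitivity. The effect on specificity, PPV and agreement is uncertain in direction, and no size can be computed from the documents.

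The conclusion rests on two readings of the text: that the operator's record made during the scan is the stage two TLUS result, and that provoked symptoms are noticeable to someone scanning the neck. Both are natural, but neither is written down. The documents show an open route for bias, not that bias will occur. It is worth closing before stage two starts, because a reading untouched by the laryngoscopy result cannot be recovered once the results have been compared.

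**What to change.** 1. **Stage two: patient population.** State that blinding does not cover provoked symptoms. Have the TLUS ILO call recorded and locked on the form before the PI learns anything of the laryngoscopy result. Require the dynamic stage two clip to be saved; the text now mentions stored images only, and the remark about silent recordings belongs to stage one.
2. **Last paragraph on stage two.** Defer the TLUS–laryngoscopy comparison until all stage two readings are locked. Until then the laryngoscopy results must be kept from the PI; as Data collection and handling stands, the PI enters the form data and alone has access to the electronic files.
3. **Before that comparison.** The PI re-reads every stage two clip in random order under a neutral code, without the recording form or the laryngoscopy result. The present participant code contains the clinic date, so it will not serve.
4. **Data analysis.** Report 2 x 2 tables for both the live call and the image-only reading, with their difference and the intra-reader agreement. With about 30 patients, treat the difference as descriptive.

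Cost: about 30 short re-reads, a later comparison and a few sentences of protocol text, with no extra staff or patient procedure. Some clips may be remembered, and the image-only accuracy may look less favourable. A reader who was not in the room, such as the collaborator or sonographer already mentioned for stage one, would avoid the memory problem at the price of that person's time.
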